6.2 Toxicity Management

The toxicity management of the AEs including AESIs consists of safety monitoring (review of AEs on an ongoing basis, and periodic/ad hoc review of safety issues by an Independent Data Monitoring Committee), and, if applicable, interruption of study drug dosing with appropriate clinical management and/or discontinuation of the subjects from study drug. The management of specific AEs and laboratory parameters is described below.

For subjects who discontinue study drug but continue study participation and are on standard of care therapies or are enrolled in the Remission-Withdrawal Period prior to retreatment, these toxicity management requirements do not apply (including alerts from the central laboratory) and any intolerability to standard of care therapies should be managed by the prescribing physician.

Serious Infections: Study drug should be interrupted if a subject develops a serious infection. Study drug may be restarted once the infection has been successfully treated. Subjects who develop active TB must be permanently discontinued from study drug.

Herpes Zoster: If a subject develops herpes zoster, consider temporarily interrupting study drug until the episode resolves.

Gastrointestinal Perforation: If a diagnosis of gastrointestinal perforation is confirmed (other than due to appendicitis or mechanical injury), the subject must be permanently discontinued from study drug.

Major cardiovascular event: For subjects who develop a major cardiovascular event (MACE; acute myocardial infarction, stroke) while on study drug, the investigator should evaluate the benefit/risk of, and discuss with the TA MD whether it is appropriate to continue study drug.

Malignancy: Subjects who develop malignancy other than localized NMSC or carcinoma in situ of the cervix must be permanently discontinued from study drug. Information including histopathological results should be queried for confirmation of the diagnosis. Periodic skin examination is recommended

for patients who are at increased risk for skin cancer. Subjects who develop malignancies should be referred to appropriate specialists and managed as per standard of care.

Muscle-related symptoms: If a subject experiences symptoms suggestive of myositis or rhabdomyolysis, consider checking CPK and aldolase with clinical management and/or study drug interruption as deemed appropriate by the treating physician.

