Thrombosis Events: Subjects who develop symptoms of thrombosis should be promptly evaluated and treated appropriately. If the diagnosis of deep vein thrombosis, pulmonary embolism or non-cardiac, non-neurologic arterial thrombosis is confirmed, the subject must be discontinued from study drug.

COVID-19: Interrupt study drug in subjects with a confirmed diagnosis of COVID-19. Consider interrupting study drug in subjects with signs and/or symptoms and suspicion of COVID-19. Study drug may be restarted once the infection has resolved, or subject is asymptomatic. The COVID-19 eCRF must be completed.

Management of Select Laboratory Abnormalities: For any given laboratory abnormality, the Investigator should assess the subject and apply the standard of care for medical evaluation and treatment following any local guidelines. Specific toxicity management guidelines for abnormal laboratory values are described in [Table 3](#) and may require a supplemental eCRF to be completed. For subjects with ongoing laboratory abnormalities which require data entry into an eCRF, an additional eCRF related to subsequent laboratory abnormalities is only required if the subject has relevant changes in history (e.g., new onset signs or symptoms) or laboratory values which have returned to normal reference range or its Baseline value followed by subsequent laboratory abnormalities meeting toxicity guidelines (considered a new event). All abnormal laboratory tests that are considered clinically significant by the Investigator will be followed to a satisfactory resolution. If a repeat test is required per protocol, the repeat testing is to occur as soon as possible.

Table 3. Specific Toxicity Management Guidelines for Abnormal Laboratory Values (for Study 1 and Study 2 and Remission-Withdrawal Period)

Laboratory Parameter	Toxicity Management Guideline

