Hemoglobin	
 • If hemoglobin < 8 g/dL, interrupt study drug dosing and confirm by repeat testing with a new sample. If confirmed, continue to withhold study drug until hemoglobin value returns to ≥ 8 g/dL. 
OR
 
 • If hemoglobin decreases ≥ 3.0 g/dL from Baseline without an alternative etiology, interrupt study drug dosing and confirm by repeat testing with new sample. 
 • If hemoglobin decreases ≥ 3.0 g/dL from Baseline and an alternative etiology is known or the hemoglobin value remains in the normal reference range, the subject may remain on study drug at the Investigator's discretion. • If confirmed, continue to withhold study drug until hemoglobin value returns to within 3.0 g/dL from Baseline.
ANC	
 • If confirmed < 1000/μL by repeat testing with new sample, interrupt study drug dosing until ANC value returns to ≥ 1000/μL. 
 • For confirmed < 500/μL, if value returns to ≥ 1000/μL, restarting study drug is allowed if there is an alternative etiology identified; documentation should include reason that rechallenge is expected to be safe for the subject. Study drug should be discontinued if no alternative etiology can be found.
ALC	
 • If confirmed < 500/μL by repeat testing with new sample, interrupt study drug dosing until ALC returns to ≥ 500/μL.
Total WBC count	
 • If confirmed < 2000/μL by repeat testing with new sample, interrupt study drug dosing until WBC count returns to ≥ 2000/μL.

Laboratory Parameter	Toxicity Management Guideline

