AST or ALT	
 • Interrupt study drug if confirmed ALT or AST > 3 × ULN by repeat testing with new sample and either a total bilirubin > 2 × ULN or an INR > 1.5. 
 • A separate blood sample for INR testing will be needed to measure INR at the time of repeat testing for ALT or AST. A repeat test of INR is not needed for determination if above toxicity management criteria are met. • If a CPK value is not available, a CPK should be drawn to exclude AST/ALT elevations related to muscle injury. • Interrupt study drug if confirmed ALT or AST > 3 × ULN by repeat testing with new sample along with new appearance of fatigue, nausea, vomiting, right upper quadrant pain or tenderness, fever, rash, and/or new-onset eosinophilia. • Interrupt study drug if confirmed ALT or AST > 5 × ULN by repeat testing with new sample for more than 2 weeks. • If ALT or AST > 8 × ULN, interrupt study drug immediately, confirm by repeat testing with a new sample, and contact the TA MD. 
Subjects with HBc Ab+ (irrespective of hepatitis B surface antibody status) and negative HBV DNA PCR testing at Screening who develop the following laboratory findings should have HBV DNA PCR testing performed within 1 week (based on initial elevated value):
 
 • ALT > 5 × ULN OR • ALT or AST > 3 × ULN if an alternative cause is not readily identified 
 • A separate blood sample for HBV DNA PCR testing will be needed at the time of repeat testing for ALT or AST. 
A positive result for HBV DNA PCR testing will require immediate interruption of study drug (unless not acceptable by local practices). Within 1 week of the first episode of a positive HBV DNA PCR test, a hepatologist consultation should occur for recommendation regarding subsequent treatment.
 
Subjects who meet any of the above criteria should be evaluated for an alternative etiology of the ALT or AST elevation and managed as medically appropriate. If applicable, the alternative etiology should be documented in the eCRF. If ALT or AST values return to the normal reference range or the Baseline value, study drug may be restarted. If restarting study drug, documentation should include reason that rechallenge is expected to be safe. If after clinically appropriate evaluation no alternative etiology for ALT or AST elevation is found or the ALT or AST elevation has not resolved or is not trending down toward normal, the subject should be discontinued from study drug.
 
For any confirmed ALT or AST elevations > 3 ULN, complete the appropriate supplemental hepatic eCRF(s).

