TB test (QuantIFERON TB Gold test [or interferon gamma release assay equivalent such as T-SPOT test] and/or local PPD skin test, if required)	✓												✓				✓			
HBV (post-Baseline tests for subjects from Japan only)	✓						✓			✓	✓	✓	✓	✓	✓	✓	✓		✓	
HLA-B27		✓																		
Study 1 (bDMARD-IR AS) blood samples for upadacitinib PK assay (only in approximately 30% of subjects in select sites)				✓		✓	✓	✓											✓	
Study 2 (nr-axSpA) blood samples for upadacitinib PK assay (only in approximately 30% of subjects in select sites)				✓		✓		✓		✓		✓							✓	
 TREATMENT																				
Randomization/drug assignment		✓																		

Activity	Screening	Baseline	Wk 1	Wk 2	Wk 4	Wk 8	Wk 12	Wk 14	Wk 18	Wk 24	Wk 32	Wk 40	Wk 52	Wk 64	Wk 76	Wk 88	Wk 104	Unscheduled Visit	PD Visit	30-Day F/U Visit OR Phone Call
		Day 1																		
Dispense study drug		✓			✓	✓	✓	✓		✓	✓	✓	✓	✓	✓	✓		✓		
Dispense study drug (subjects entering OLE for applicable countries; see Appendix F)																	✓			

Optional Biomarker Sample Activities Table (Applicable for Study 1 and Study 2)

Activity	Screening	Baseline	Wk 1	Wk 2	Wk 4	Wk 8	Wk 12	Wk 14	Wk 18	Wk 24	Wk 32	Wk 40	Wk 52	Wk 64	Wk 76	Wk 88	Wk 104	Unscheduled Visit	PD Visit	30-Day F/U Visit OR Phone Call
		Day 1																		
Study 1 (bDMARD-IR AS) blood: (DNA/RNA/serum/plasma)		✓		✓				✓												
Study 2 (nr-axSpA) blood: (DNA/RNA/serum/plasma)		✓		✓				✓					✓							

Study Activities Table for Remission-Withdrawal Period (Prior to Retreatment)

Activity	Wk 110	Wk 116	Wk 122	Wk 128	Wk 140	Wk 152	Unscheduled Visit	PD Visit
INTERVIEWS & QUESTIONNAIRES								
Concomitant therapy	✓	✓	✓	✓	✓	✓	✓	✓
Review and document pregnancy avoidance recommendations with females of childbearing potential	✓	✓	✓	✓	✓	✓	✓	✓
PRO								
BASDAI, PtGA, Total Back Pain, BASFI, Patient's Global Assessment of Pain, Nocturnal Back Pain, ASAS HI	✓	✓	✓	✓	✓	✓	✓	✓
EXAM								
Body weight	✓	✓	✓	✓	✓	✓	✓	✓
Vital signs	✓	✓	✓	✓	✓	✓	✓	✓
Physical Exam				✓		✓		
AE assessment	✓	✓	✓	✓	✓	✓	✓	✓
Investigator assessments: TJC/SJC, BASMI _{in} , MASES, PGA	✓	✓	✓	✓	✓	✓	✓	✓
ASDAS (CRP) calculation to determine disease status	✓	✓	✓	✓	✓	✓	✓	
LOCAL LAB								
Erythrocyte sedimentation rate	✓	✓	✓	✓	✓	✓	✓	✓
Urine pregnancy test (for all female subjects of childbearing potential entering OLE for applicable countries; see Appendix F)						✓		

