Dispense urine pregnancy tests for monthly home testing (subjects entering OLE for applicable countries; see Appendix F)						✓		

Activity	Wk 110	Wk 116	Wk 122	Wk 128	Wk 140	Wk 152	Unscheduled Visit	PD Visit
								
hsCRP	✓	✓	✓	✓	✓	✓	✓	✓
Clinical chemistry, hematology, urinalysis	✓	✓	✓	✓	✓	✓	✓	✓
HBV (post-Baseline tests for subjects from Japan only)		✓		✓	✓	✓		

Study Activities Table for Remission-Withdrawal Period (After Retreatment)

Activity	RT Baseline	RT Wk 4	RT Wk 8	RT Wk 12	RT Wk 16	RT Wk 24	RT PD Visit	RT 30-Day F/U Visit OR Phone Call
INTERVIEWS & QUESTIONNAIRES								
Concomitant therapy		✓	✓	✓	✓	✓	✓	✓
Review and document pregnancy avoidance recommendations with females of childbearing potential	✓	✓	✓	✓	✓	✓	✓	✓
Latent TB risk assessment questionnaire	Annually, at a retreatment visit that is closest to Week 156, if applicable							
PRO								
BASDAI, Total Back Pain, BASFI, PtGA, Patient's Global Assessment of Pain, Nocturnal Back Pain, ASAS HI		✓	✓	✓	✓	✓	✓	
Subject Diary	✓	✓	✓	✓	✓	✓	✓	
EXAM								
Body weight		✓	✓	✓	✓	✓	✓	
Vital Signs		✓	✓	✓	✓	✓	✓	
Physical Exam				✓		✓		
AE Assessment		✓	✓	✓	✓	✓	✓	✓
Investigator Assessments: BASMI _{lin} , MASES, PGA, TJC/SJC				✓		✓	✓	
CXR (annually if annual TB test is newly positive [seroconversion] or a positive response to TB risk assessment questionnaire)	Annually, at a retreatment visit that is closest to Week 156, if applicable							
LOCAL LAB								
Urine pregnancy test (for all female subjects of childbearing potential)	✓	✓	✓	✓	✓	✓	✓	
Dispense urine pregnancy tests for monthly home testing					✓			

Activity	RT Baseline	RT Wk 4	RT Wk 8	RT Wk 12	RT Wk 16	RT Wk 24	RT PD Visit	RT 30-Day F/U Visit OR Phone Call
Dispense urine pregnancy tests for monthly home testing (subjects entering OLE for applicable countries; see Appendix F)						✓		
Erythrocyte sedimentation rate		✓	✓	✓	✓	✓	✓	
 CENTRAL LAB								
hsCRP, clinical chemistry, hematology, urinalysis		✓	✓	✓	✓	✓	✓	
HBV (post-Baseline tests for subjects from Japan only)				✓		✓		
TB test (QuantIFERON TB Gold test [or interferon gamma release assay equivalent such as T-SPOT test] and/or local PPD skin test, if required)	Annually, at a retreatment visit that is closest to Week 156, if applicable							
 TREATMENT								
Dispense Study Drug	✓			✓				

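### The flare-visit safety sample, the last one scheduled before upadacitinib is restarted, carries no central-laboratory alert and no explicit requirement for a Table 3 review before dispensing

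*Protocol*

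**What the plan says.** Section 6.2 lifts the toxicity rules for two groups. One is subjects who have stopped study drug and moved to standard of care. The other is subjects who "are enrolled in the Remission-Withdrawal Period prior to retreatment, these toxicity management requirements do not apply (including alerts from the central laboratory"). The sentence ends by leaving intolerability of standard-of-care therapies to the prescribing physician.

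Appendix D has two tables for this period. The table for the time before re-treatment schedules "Clinical chemistry, hematology, urinalysis" at Weeks 110, 116, 122, 128, 140 and 152, at unscheduled visits and at premature discontinuation. At the same visits, apart from premature discontinuation, it schedules "ASDAS (CRP) calculation to determine disease status". The table for the time after re-treatment lists four activities at RT Baseline: pregnancy-avoidance review, subject diary, urine pregnancy test and drug dispensing.

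Section 4.1 starts re-treatment at the time of flare. The synopsis describes flaring subjects as eligible for re-treatment. Neither sets a laboratory condition.

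For subjects on drug, Table 3 in Section 6.2 does set conditions. For hemoglobin: "If hemoglobin < 8 g/dL, interrupt study drug dosing and confirm by repeat testing with a new sample". For ALT or AST above 8 × ULN: "interrupt study drug immediately, confirm by repeat testing with a new sample, and contact the TA MD". After an ALT or AST interruption, drug may be restarted once values are back to normal or Baseline, and "If restarting study drug, documentation should include reason that rechallenge is expected to be safe".

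**The concern.** Off drug, the waiver makes sense: there is no dosing to interrupt. It stops making sense at one moment, the decision to restart. The waiver runs until re-treatment begins, so it also covers the sample drawn at the visit that triggers re-treatment. Section 2.2 lists falls in hemoglobin, changes in lymphocyte count and rises in transaminases among the laboratory changes observed with upadacitinib. These are parameters for which Table 3 interrupts dosing.

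At stake is the safety of re-treated subjects. A value that would stop dosing in a subject on drug could be present at the flare visit without prompting an alert or a required check. Dosing could then run for about four weeks before the next scheduled sample that carries an alert.

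**Working it through.** The plan gives no figure to reproduce. The check sets Section 6.2 beside the two Remission-Withdrawal tables in Appendix D and adds visit arithmetic.

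**1. What is checked, and when**

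| | Flare-establishing visit | RT Baseline | RT Week 4 |
|---|---|---|---|
| Chemistry and hematology | yes | no | yes |
| Vital signs | yes | no | yes |
| Adverse-event assessment | yes | no | yes |
| Concomitant therapy | yes | no | yes |
| Study drug dispensed | no | yes | no |
| Section 6.2 rules and alerts in force | no | only once re-treatment starts | yes |

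The flare-visit sample is therefore the last scheduled safety sample before restart, and it falls inside the waiver.

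**2. Dosing before the next alert-covered sample**

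- Dosing is once daily and the next sample is at RT Week 4: 4 × 7 = 28 doses.
- Section 4.1 allows ± 7 days for visits after Week 14. Assuming this extends to re-treatment visits: 28 − 7 = 21 to 28 + 7 = 35 doses.

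**3. Time between scheduled alert-covered samples**

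The last scheduled sample before withdrawal is Week 104. If re-treatment starts at the flare visit:

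- flare at Week 110 on a single ASDAS above 3.5: (110 − 104) + 4 = 10 weeks;
- flare at Week 152: (152 − 104) + 4 = 52 weeks.

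**4. What a Table 3 check could change**

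Table 3 has 6 rows: hemoglobin, ANC, ALC, WBC, AST/ALT and creatinine. A single value can interrupt dosing in 2 of them. These are hemoglobin (below 8 g/dL, or a fall of at least 3.0 g/dL without another cause) and AST/ALT (above 8 × ULN). The other 6 − 2 = 4 rows need a confirming repeat first. In the hemoglobin row, a fall of that size leaves continuation to the Investigator if another cause is known or the value is still in the normal range.

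**5. Whether another stated rule requires the review**

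- The laboratory entry limits (criterion 24) apply in the Screening Period only.
- Criterion 34, on suitability to receive study drug, is a judgment. Eligibility is ticked at Week 104, not at RT Baseline.
- Section 5.5 lets the Investigator or sponsor physician stop drug for abnormal results, but it is framed around continuing treatment.
- Section 6.1 gives a general duty to monitor for clinical and laboratory evidence of adverse events.
- Section 5.3 prohibits strong CYP3A inhibitors and inducers in this period only while study drug is taken. One started during withdrawal would have to be noticed at restart, and RT Baseline has no concomitant-therapy check.

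None of these requires the flare-visit values to be compared with Table 3 before dispensing.

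**The case against.** The strongest reply is that little is really missing.

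- **The results exist and reach the site.** Flare is defined by ASDAS (CRP), so the site needs the hsCRP from the visit at which the safety panel is drawn. A reader might infer that subjects are restarted blind. The documents do not support that. That the two results are read together is likely, but it is not required.
- **Table 3 comes back into force.** Its title names the Remission-Withdrawal Period and the waiver ends at re-treatment, so a known hemoglobin below 8 g/dL would call for interruption once dosing starts. This stands. It acts after the first dose, however, and only if someone has looked.
- **Ordinary care continues.** Section 6.2 also says: "For any given laboratory abnormality, the Investigator should assess the subject and apply the standard of care for medical evaluation and treatment". Because that sentence sits in the waived section, a reader might infer that it is switched off too. That stretches a waiver aimed at drug-interruption rules and alerts. The better reading is that ordinary care arguably remains, but the sentence sets no threshold and no hold on dosing.
- **The blank cells avoid duplication.** Section 3.4 places the re-treatment baseline at the time of flare, and the panel has already been drawn. This is a fair reason not to add a blood draw. It does not supply the missing review.
- **Four weeks is not long in this protocol.** Study 2 placebo subjects who start upadacitinib at Week 52 are next sampled at Week 64, 12 weeks later. That is correct, but their Week 52 sample is not covered by the waiver.
- **The DMC reviews safety data.** Its review is periodic and does not control an individual restart.
- **The operations manual may contain a pre-dose check.** Appendix D says it describes the activities in detail. It was not supplied, so the gap can be asserted only for the text reviewed.

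**Conclusion.** The point holds in limited form. An explicit waiver, not just missing detail, leaves the last scheduled pre-restart sample without an alert and without a stated requirement for review against Table 3 before dispensing. The next scheduled alert-covered sample follows about 28 doses, or 21 to 35 if the visit window applies.

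A reader might go further and infer that every re-treated subject is at risk. Every re-treated subject passes through this step, but harm needs a Table 3 abnormality while off drug that the Investigator also overlooks. The documents do not say how many subjects will flare or have such a value.

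Severity is low to moderate. The conclusion assumes that the operations manual adds no pre-dose check.

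**What to change.** 1. Amend Section 6.2 so that neither the waiver nor the alert switch-off covers the sample from the visit that establishes flare.
2. Add to the RT Baseline instructions that, before dispensing, the Investigator reviews that sample against Table 3, together with the adverse events and concomitant therapy recorded at that visit.
3. Apply Table 3 as if the subject were on drug. Repeat a value only if it meets a threshold. Keep the hemoglobin discretion for a known alternative cause or a value in the normal range. Hold the first re-treatment dose until Table 3's own restart condition is met; for ALT or AST, that is a return to normal or Baseline with a documented reason that rechallenge is safe. A stricter hold would treat these subjects differently from subjects on drug, without a stated reason.

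If the operations manual already requires this review, a cross-reference to it and change 1 would be enough.

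The cost is a wording change, a few extra alerts, and an occasional short delay of re-treatment for a subject in flare. No routine extra sample is needed, because the safety panel is already drawn with the hsCRP used to establish flare.

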6.3 Data Monitoring Committee

For each study, an independent, external DMC will be established for periodic review of unblinded safety data and to alert AbbVie to possible safety concerns related to the conduct of the study to ensure subject safety. If necessary to ensure subject safety, the DMC will also be given access to selected efficacy data which will be specified in the DMC charter.

The DMC charter will describe the roles and responsibilities of the DMC members, frequency of data reviews, and relevant data to be assessed. Communications from the DMC to the Study Team will not contain information that could potentially unblind the team to subject treatment assignments.

7 STATISTICAL METHODS & DETERMINATION OF SAMPLE SIZE

7.1 Statistical and Analytical Plans

Study 1 (bDMARD-IR AS) and Study 2 (nr-axSpA) will be analyzed separately for global submission purposes. The AbbVie study team will be unblinded to perform the primary analysis and reporting for each study independently.

For Study 1 (bDMARD-IR AS), the database lock for the primary analysis will occur after all Study 1 subjects have completed the Week 14 visit or have prematurely discontinued prior to Week 14.

For Study 2 (nr-axSpA), the database lock for the primary analysis will occur after all Study 2 subjects have completed the Week 14 visit or have prematurely discontinued prior to Week 14.

The primary analysis for Study 1 and Study 2 will be conducted for the comparisons of the upadacitinib group versus the placebo group. The database lock dates may be different for Study 1 and Study 2. For Study 1 and Study 2, sites and subjects will remain blinded to the placebo-controlled period treatment assignments for the duration of the respective study.

Additional analyses will also be conducted for each study independently as follows:

- For Study 1 (bDMARD-IR AS), an analysis will be conducted when all subjects in the study have completed the Week 104 visit or have prematurely discontinued prior to Week 104. An additional analysis may be conducted for regulatory purposes after all subjects have completed the Week 52 visit or have prematurely discontinued prior to Week 52.
- For Study 2 (nr-axSpA), an analysis will be conducted after all subjects in the study have completed the Week 104 visit or have prematurely discontinued prior to Week 104. An additional analysis will be conducted for regulatory purposes after all subjects have completed the Week 52 visit or have prematurely discontinued prior to Week 52.

Specific details of the statistical analyses will be described and fully documented in the Statistical Analysis Plan (SAP) for each study. For both studies, the SAP will be finalized prior to the Week 14 database lock of the study. The statistical analyses will be performed using SAS (SAS Institute Inc., Cary, North Carolina, USA).

